2.2. Endpoints

2.2.1. Primary Endpoint

- ORR, which includes confirmed best response of CR or PR as assessed by the Investigator

2.2.2. Key Secondary Endpoint

- DOR, defined as the time from initial Investigator-assessed response (CR or PR) until progressive disease (PD) as assessed by the Investigator

2.2.3. Additional Secondary Endpoints

- TEAEs and laboratory test results, physical examination, or vital signs
- CA-125 response determined using the Gynecologic Cancer Intergroup (GCIG) criteria defined in [Appendix C](#)
- PFS, defined as the time from first dose of MIRV until Investigator-assessed radiological PD or death, whichever occurs first
- OS, defined as the time from first dose of MIRV until death
- ORR, DOR, and PFS by blinded independent central review (BICR) will be summarized as sensitivity analysis

2.2.4. Exploratory Endpoints

Exploratory endpoints are provided below. The analysis and subsequent results of these assessments may be reported in separate documents and not included in the statistical analysis plan (SAP) or clinical study report, respectively.

- Incidence of seroconversion of antidrug antibodies (ADA) to MIRV and association with safety and efficacy
- Identification of blood-based biomarkers potentially predictive of responsiveness to treatment
- Identification of tumor DNA mutational status and the expression level of genes and pathways involved in cancer development, progression, and responsiveness to treatment
- Correlation of gene mutation(s) and/or homologous recombination status with tumor FR α levels and soluble FR α levels in blood

Document ID: CLIN-00067	Title: IMGN853-0419 Clinical Study Protocol	Version: 2.0
Legacy ID: 26587		Approved Date: 12/22/202

3. STUDY POPULATION

3.1. Criteria for Selection of Patient Population

3.1.1. Inclusion Criteria

1. Patients \geq 18 years of age
2. Patients must have an Eastern Cooperative Oncology Group Performance Status (ECOG PS) of 0 or 1
3. Patients must have a confirmed diagnosis of high-grade serous EOC, primary peritoneal cancer, or fallopian tube cancer
4. Patients must have platinum-sensitive disease defined as radiographic progression greater than 6 months from last dose of most recent platinum therapy

Note: Progression should be calculated from the date of the last administered dose of platinum therapy to the date of the radiographic imaging showing progression

5. Patients must have progressed radiographically on or after their most recent line of anticancer therapy
6. Patients must have at least 1 lesion that meets the definition of measurable disease by Response Evaluation Criteria in Solid Tumors version 1.1 (RECIST v1.1) (radiologically measured by the Investigator)
7. Patients must be willing to provide an archival tumor tissue block or slides, or undergo procedure to obtain a new biopsy using a low-risk, medically routine procedure for immunohistochemistry (IHC) confirmation of FR α positivity
8. Patient's tumor must be positive for FR α expression as defined by the Ventana FOLR1 Assay
9. Prior anticancer therapy

- a. Patients must have received at least 2 prior systemic lines of platinum therapy and be considered by the Investigator as appropriate for single-agent non-platinum therapy (documentation required – eg, high risk of hypersensitivity reaction; risk of further cumulative toxicity with additional platinum, including but not limited to myelosuppression, neuropathy, renal insufficiency or other)

Note: Patients who have had a documented platinum allergy may have had only 1 prior line of platinum

- b. Patients may have received up to but no more than 1 prior independent non-platinum cytotoxic therapy
- c. Patients must have had testing for *BRCA* mutation (tumor or germline) and, if positive, must have received a prior PARP inhibitor as either treatment or maintenance therapy
- d. Neoadjuvant \pm adjuvant therapies are considered 1 line of therapy
- e. Maintenance therapy (eg, bevacizumab, PARP inhibitors) will be considered part of the preceding line of therapy (ie, not counted independently)

Document ID: CLIN-00067	Title: IMGN853-0419 Clinical Study Protocol	Version: 2.0
Legacy ID: 26587		Approved Date: 12/22/202

- f. Therapy changed due to toxicity in the absence of progression will be considered part of the same line (ie, not counted independently)

10. Patients must have completed prior therapy within the specified times below:

- a. Systemic antineoplastic therapy within 5 half-lives or 4 weeks (whichever is shorter) prior to first dose of MIRV
- b. Focal radiation completed at least 2 weeks prior to first dose of MIRV

11. Patients must have stabilized or recovered (Grade 1 or baseline) from all prior therapy-related toxicities (except alopecia)

12. Patients must have completed any major surgery at least 4 weeks prior to first dose of MIRV and have recovered or stabilized from the side effects of prior surgery prior to first dose of MIRV

13. Patients must have adequate hematologic, liver and kidney functions defined as:

- a. Absolute neutrophil count (ANC) $\geq 1.5 \times 10^9/L$ ($1500/\mu L$) without granulocyte colony-stimulating factor (G-CSF) in the prior 10 days or long-acting white blood cell (WBC) growth factors in the prior 20 days
- b. Platelet count $\geq 100 \times 10^9/L$ ($100,000/\mu L$) without platelet transfusion in the prior 10 days
- c. Hemoglobin $\geq 9.0 \text{ g/dL}$ without packed red blood cell (PRBC) transfusion in the prior 21 days
- d. Serum creatinine $\leq 1.5 \times$ upper limit of normal (ULN)
- e. Aspartate aminotransferase (AST) and alanine aminotransferase (ALT) $\leq 3.0 \times$ ULN
- f. Serum bilirubin $\leq 1.5 \times$ ULN (patients with documented diagnosis of Gilbert syndrome are eligible if total bilirubin $< 3.0 \times$ ULN)
- g. Serum albumin $\geq 2 \text{ g/dL}$

14. Patients must be willing and able to sign the informed consent form (ICF) and to adhere to the protocol requirements

15. Women of childbearing potential (WCBP) must agree to use highly effective contraceptive method(s) while on MIRV and for at least 3 months after the last dose

16. WCBP must have a negative pregnancy test within the 4 days prior to the first dose of MIRV

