1.5.3. Conclusion

Safety and efficacy data were available in 737 patients who received MIRV as a single-agent or in combination and are consistent with a positive risk benefit assessment. The potential benefit of the antitumor activity demonstrated by MIRV in patients with FR α high, recurrent platinum-sensitive EOC with at least 2 prior lines of therapy, a population with high unmet need, outweighs the risks associated with the well tolerated safety profile, as summarized above.

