4. INVESTIGATIONAL PLAN

4.1. Study Design

4.1.1. Overview and Schema

This Phase 2 study is designed to evaluate the efficacy and safety of MIRV in patients with recurrent platinum-sensitive, high-grade serous EOC, primary peritoneal, or fallopian tube cancer, whose tumors express a high level of FR α . Patients will have had at least 2 prior lines of therapy. These will include at least 2 lines of platinum-containing therapy or 1 line with a documented platinum allergy. All patients will be, in the opinion of the Investigator, appropriate for non-platinum single-agent therapy for their next line of therapy. FR α positivity will be defined by the Ventana FOLR1 (FOLR1-2.1) CDx assay (Ventana FOLR1 Assay).

The study is designed to test the null hypothesis that the ORR is $\leq 28\%$ using an optimal Simon's two-stage design ([Simon 1989](#)) without a planned pause in enrollment given preliminary efficacy and established safety of MIRV. Approximately 75 patients will be enrolled so that a total of 69 patients will be efficacy evaluable.

Efficacy evaluable patients include those who have at least 1 measurable lesion (per RECIST v1.1) at baseline and received at least 1 dose of MIRV.

All patients will receive single-agent MIRV at 6 mg/kg AIBW ([Appendix D](#)) administered through IV infusion on Day 1 of every 3-week cycle (Q3W).

Computerized tomography (CT) or magnetic resonance imaging (MRI) scans will be collected for sensitivity analysis by BICR.

Patients will continue to receive MIRV until PD, unacceptable toxicity, withdrawal of consent, death, or until the Sponsor terminates the study (whichever comes first).

Tumor assessments, including radiological assessment by CT/MRI scans, will be performed at Screening and subsequently every 6 weeks (± 1 week) from Cycle 1 Day 1 (C1D1) for the first 36 weeks then every 12 weeks (± 3 weeks) until PD, death, the start of new anticancer therapy, or patient's withdrawal of consent, whichever occurs first.

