4.12.5. Per Protocol Population

The per protocol population is defined as all patients who have received at least 1 dose of MIRV, excluding patients with protocol deviations in the following categories: Patients -

- whose tumors do not have FR α positivity as defined by the Ventana FOLR1 Assay and/or
- patients without a documented platinum allergy who had only 1 prior line of platinum, and/or
- who do not meet the eligibility criterion of being platinum sensitive, and/or
- other critical/major protocol deviations that deemed affecting primary and/or key secondary objectives. The final list of critical/major protocol deviations leading to the removal of patients from the per protocol population will be finalized and signed off before the database lock for the final ORR analysis.

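### No inclusion criterion enforces the stated minimum of 2 prior lines of therapy, so a platinum-allergic patient with a single prior line can enter the primary ORR

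*Protocol*

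**What the plan says.** Protocol 4.1.1, repeated in the synopsis and SAP 3.2, sets two conditions. The first is on the total: "Patients will have had at least 2 prior lines of therapy". The second is on platinum content: "These will include at least 2 lines of platinum-containing therapy or 1 line with a documented platinum allergy". Protocol 1.5.3 draws its benefit-risk conclusion for "recurrent platinum-sensitive EOC with at least 2 prior lines of therapy, a population with high unmet need".

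The inclusion criteria (Protocol 3.1.1 and synopsis) are worded differently. Criterion 9a says "Patients must have received at least 2 prior systemic lines of platinum therapy", and its Note adds "Note: Patients who have had a documented platinum allergy may have had only 1 prior line of platinum". Criterion 9b says "Patients may have received up to but no more than 1 prior independent non-platinum cytotoxic therapy". Criteria 9d to 9f count neoadjuvant and adjuvant treatment as one line, attach maintenance to the line before it, and keep a switch for toxicity without progression within the same line.

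On the analysis side, Protocol 10 and SAP 4.12.3 define the Efficacy Evaluable Population by at least one dose and measurable disease at baseline. SAP 4.12.5 excludes from the per-protocol population "patients without a documented platinum allergy who had only 1 prior line of platinum", among other categories. SAP 6.4 lists number of prior lines as a subgroup, without categories.

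**The concern.** In the design text the allergy exception relaxes how many of the prior lines must be platinum. It does not relax the total. In the criteria the total has disappeared, and the same exception becomes a route to enrolment after one line. Protocol 12.7 makes investigators responsible for enrolling only patients who meet the eligibility criteria, so sites will work from the numbered list.

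In a single-arm trial judged against a fixed 28%, the population enrolled determines what the ORR means. The unmet need (1.3), the supporting data in 11 patients (1.5.1) and the benefit-risk conclusion (1.5.3) all refer to patients with two or more prior lines. Section 1.3 also says that response to chemotherapy falls with each line. If one-line patients are included and not identified, the reported ORR belongs to a broader group than the one for which the case is made.

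**Working it through.** **1. Can a one-line patient satisfy the criteria?** Take a patient with a documented platinum allergy, one prior platinum line, and radiographic progression more than 6 months after the last platinum dose.

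- Criterion 4 (platinum-sensitive): met.
- Criterion 5 (radiographic progression on or after the most recent line): met.
- Criterion 9a: the Note waives the second platinum line. Hypersensitivity risk is one of the listed reasons for considering non-platinum single-agent therapy appropriate.
- Criterion 9b: a ceiling of one non-platinum cytotoxic therapy, with no minimum. Zero is allowed.
- Criterion 9c: if *BRCA* positive, PARP inhibitor maintenance satisfies it, and under 9e that adds no line.
- Criterion 9f: a change of drug forced by an allergic reaction, without progression, stays in the same line.

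Nothing in 9a to 9f requires a second line. The single line must be platinum.

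**2. Does the analysis remove or show her?**

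| Place | Effect |
|---|---|
| Protocol 10, SAP 4.12.3 (primary ORR) | Included; no condition on lines |
| SAP 4.12.5, one-platinum-line exclusion | Does not apply; she has an allergy |
| SAP 4.12.5, other critical/major deviations | Could apply, at discretion |
| SAP 6.4, number of prior lines | No cut-points; she may be pooled |

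**3. Reproduce the design.** Inputs (Protocol 10.1): n1 = 28, stop if 9 or fewer respond; n = 69, reject if more than 26 respond; null 28%, alternative 48%.

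- Early termination = P(X1 ≤ 9 | 28, p). At p = 0.28 this is 0.7624 (stated 0.762).
- Expected N = 28 + (1 − 0.7624) × 41 = 37.74 (stated 37.74).
- P(reject) = Σ over x1 = 10 to 28 of P(X1 = x1) × P(X2 > 26 − x1 | 41, p). At p = 0.28 this is 0.0245, or 0.024493 before rounding (stated 0.024). At p = 0.48 it is 0.900 (stated 0.9).

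**4. Effect of a share f of one-line patients.** Hold all other patients at the 28% null and give one-line patients rate q, so that p = 0.28(1 − f) + q·f. The documents give no value for f and no MIRV response rate by line. Both f values below are assumptions: 0.05 × 69 is about 3 patients and 0.10 × 69 about 7.

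| q | Source of q | p, f = 5% | P(reject) | p, f = 10% | P(reject) |
|---|---|---|---|---|---|
| 29% | Protocol 1.3, upper figure for second-line single agents in platinum-sensitive disease | 0.2805 | 0.0250 | 0.281 | 0.0256 |
| 40% | assumed | 0.286 | 0.032 | 0.292 | 0.040 |
| 48% | assumed (equals the design alternative) | 0.290 | 0.037 | 0.300 | 0.055 |
| 56% | assumed | 0.294 | 0.044 | 0.308 | 0.073 |

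At q = 28% the error stays at 0.0245 for any f.

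**5. The protocol's own chemotherapy rates in both groups.** With 13% after two prior lines and 29% in the second line, the mixed rate reaches 28% only when f = (0.28 − 0.13)/(0.29 − 0.13) = 0.94. At f = 10% it is 0.146, and P(reject) is below 0.000001.

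**The case against.** The strongest reply concerns impact. A reader might infer that one-line patients will raise the observed ORR and so inflate the type I error. The documents do not support that as a statement of fact. The fall from 28-29% to 10-13% in Protocol 1.3 is for topotecan and paclitaxel, and no gradient by line is given for MIRV. The 28% null equals the lower end of the second-line figure and lies well above the later-line one, so on the protocol's own rates a few one-line patients do not make the test anti-conservative. A rate of 56% appears in 1.3 only for second-line platinum doublets, which is a different treatment setting. This objection stands.

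The number of such patients may also be small. Section 1.3 ties platinum hypersensitivity to cumulative exposure, and nothing in the documents supports either 5% or 10%. This stands too.

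The SAP is not silent. The discretionary bullet in 4.12.5 could be used, because 12.7 requires adherence to the protocol as a whole. SAP 5.1.4 tabulates prior systemic therapies and platinum lines, and 6.4 plans a subgroup by number of prior lines. This stands in part. A patient who meets every criterion is not clearly a deviation, and 5.1.4 counts distinct regimens, which need not match the line count under 9d to 9f. A subgroup without cut-points does not guarantee a one-line category.

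Finally, the sponsor may have meant to admit allergic patients after one line. That is possible, but the design text and 1.5.3 would then need correcting. The inconsistency remains either way.

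**Conclusion.** The inconsistency holds on the text alone. The stated population has at least 2 prior lines in total, the criteria do not require it, and a one-line platinum-allergic patient can be enrolled and counted in the primary ORR. No planned analysis is certain to exclude her or show her separately.

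The consequence is one of interpretation: the ORR may not describe the population for which unmet need and benefit-risk are argued. A claim of type I error inflation goes further than the documents allow. Against 2.4% as designed, the error is 2.5-2.6% if one-line patients respond at 29%, and 3.2-7.3% only if they respond at an assumed 40-56%. Both ranges take 5-10% of patients as one-line, which is also assumed, and hold everyone else exactly at 28%. The design's stated operating characteristics are correct and are not affected by the fix.

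**What to change.** Reconcile the 9a Note (Protocol 3.1.1 and synopsis) with Protocol 4.1.1, 1.5.3 and SAP 3.2, so that eligibility and the stated population carry the same requirement on total prior lines, counted under 9d to 9f. The sponsor should say which was intended.

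In the SAP, whichever way this is settled:

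- Give the number-of-prior-lines subgroup in 6.4 explicit categories, including one prior line, counted under 9d to 9f.
- Add to 6.5 a sensitivity analysis of ORR excluding patients with fewer than 2 prior lines. This fits better than a further per-protocol exclusion, because these patients may have no eligibility deviation.

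The cost is one clause in the protocol and one small extra analysis. If the criteria are brought into line with the design text, a few allergic patients with one prior line become ineligible. Sample size and decision rule do not change.

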Note: Patients who have had a documented platinum allergy may have had only 1 prior line of platinum
 - b. Patients may have received up to but no more than 1 prior independent non-platinum cytotoxic therapy
 - c. Patients must have had testing for breast cancer susceptibility gene (*BRCA*) mutation (tumor or germline) and, if positive, must have received a prior poly (ADP-ribose) polymerase (PARP) inhibitor as either treatment or maintenance therapy
 - d. Neoadjuvant \pm adjuvant therapies are considered 1 line of therapy
 - e. Maintenance therapy (eg, bevacizumab, PARP inhibitors) will be considered part of the preceding line of therapy (ie, not counted independently)
 - f. Therapy changed due to toxicity in the absence of progression will be considered part of the same line (ie, not counted independently)
10. Patients must have completed prior therapy within the specified times below:
 - a. Systemic antineoplastic therapy within 5 half-lives or 4 weeks (whichever is shorter) prior to first dose of MIRV
 - b. Focal radiation completed at least 2 weeks prior to first dose of MIRV
11. Patients must have stabilized or recovered (Grade 1 or baseline) from all prior therapy-related toxicities (except alopecia)
12. Patients must have completed any major surgery at least 4 weeks prior to first dose of MIRV and have recovered or stabilized from the side effects of prior surgery prior to first dose of MIRV
13. Patients must have adequate hematologic, liver and kidney functions defined as:
 - a. Absolute neutrophil count (ANC) $\geq 1.5 \times 10^9/L$ ($1500/\mu L$) without granulocyte colony-stimulating factor (G-CSF) in the prior 10 days or long-acting white blood cell (WBC) growth factors in the prior 20 days
 - b. Platelet count $\geq 100 \times 10^9/L$ ($100,000/\mu L$) without platelet transfusion in the prior 10 days
 - c. Hemoglobin $\geq 9.0 \text{ g/dL}$ without packed red blood cell (PRBC) transfusion in the prior 21 days
 - d. Serum creatinine $\leq 1.5 \times$ upper limit of normal (ULN)
 - e. Aspartate aminotransferase (AST) and alanine aminotransferase (ALT) $\leq 3.0 \times$ ULN

- f. Serum bilirubin \leq 1.5 x ULN (patients with documented diagnosis of Gilbert syndrome are eligible if total bilirubin $<$ 3.0 x ULN)
- g. Serum albumin \geq 2 g/dL
- 14. Patients must be willing and able to sign the informed consent form (ICF) and to adhere to the protocol requirements

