3.1.2. Exclusion Criteria

- 1. Patients with endometrioid, clear cell, mucinous, or sarcomatous histology, mixed tumors containing any of the above histologies, or low-grade/borderline ovarian tumor
- 2. Patients with prior wide-field radiotherapy (RT) affecting at least 20% of the bone marrow
- 3. Patients with > Grade 1 peripheral neuropathy per Common Terminology Criteria for Adverse Events (CTCAE)
- 4. Patients with active or chronic corneal disorders, history of corneal transplantation, or active ocular conditions requiring ongoing treatment/monitoring, such as uncontrolled

Document ID: CLIN-00067	Title: IMGN853-0419 Clinical Study Protocol	Version: 2.0
Legacy ID: 26587		Approved Date: 12/22/202

glaucoma, wet age-related macular degeneration requiring intravitreal injections, active diabetic retinopathy with macular edema, macular degeneration, presence of papilledema, and/or monocular vision

5. Patients with serious concurrent illness or clinically relevant active infection, including, but not limited to the following:
 - a. Active hepatitis B or C infection (whether or not on active antiviral therapy)
 - b. HIV infection
 - c. Active cytomegalovirus infection
 - d. Any other concurrent infectious disease requiring IV antibiotics within 2 weeks prior to the first dose of MIRV

Note: Testing at screening is not required for the above infections unless clinically indicated.

6. Patients with a history of multiple sclerosis (MS) or other demyelinating disease and/or Lambert-Eaton syndrome (paraneoplastic syndrome)
7. Patients with clinically significant cardiac disease including, but not limited to, any of the following:
 - a. Myocardial infarction \leq 6 months prior to first dose
 - b. Unstable angina pectoris
 - c. Uncontrolled congestive heart failure (New York Heart Association > class II)
 - d. Uncontrolled \geq Grade 3 hypertension (per CTCAE)
 - e. Uncontrolled cardiac arrhythmias
8. Patients with a history of hemorrhagic or ischemic stroke within 6 months prior to enrollment
9. Patients with a history of cirrhotic liver disease (Child-Pugh Class B or C)
10. Patients with a previous clinical diagnosis of noninfectious interstitial lung disease (ILD), including noninfectious pneumonitis
11. Patients requiring use of folate-containing supplements (eg, folate deficiency)
12. Patients with prior hypersensitivity to monoclonal antibodies (mAb)
13. Women who are pregnant or breastfeeding

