12.7. Protocol Adherence

Each Investigator must adhere to the protocol as detailed in this document and agree that any changes to the protocol must be approved by ImmunoGen's authorized representative in writing before seeking approval, where necessary, from the IRB/IEC, Research Ethics Committee (REC), or Ethics Review Board (ERB). Each Investigator will be responsible for allowing only those patients who have met protocol eligibility criteria to be enrolled.

Modifications to the protocol should not be made without agreement of the Investigators and ImmunoGen. Changes to the protocol will require written IRB/IEC, REC, or ERB approval/favorable opinion before implementation, except when the modification is needed to eliminate an immediate hazard(s) to patients. The IRB/IEC/REC/ERB may provide expedited review and approval/favorable opinion for minor change(s) in ongoing studies that have the approval/favorable opinion of the IRB/IEC/REC/ERB. ImmunoGen will submit all protocol modifications to the appropriate regulatory authorities in accordance with the governing regulations.

When immediate deviation from the protocol is required to eliminate an immediate hazard(s) to patients, the Investigator will contact ImmunoGen, if circumstances permit, to discuss the planned course of action. Any departures from the protocol must be fully documented in the source documentation.

Prospective waivers or exemptions are not permitted.

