5.2.3. Protocol Deviations and Population Inclusions

Protocol deviations will be captured in a protocol deviation log. A listing of patients with any protocol deviation will be provided for the Safety population.

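### Inclusion criterion 10a sets a maximum gap since prior systemic therapy where a minimum washout was almost certainly meant

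*Protocol*

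**What the plan says.** Criterion 10 opens with "Patients must have completed prior therapy within the specified times below". Item 10a then gives the interval for systemic treatment: "Systemic antineoplastic therapy within 5 half-lives or 4 weeks (whichever is shorter) prior to first dose of MIRV". Item 10b, under the same lead-in, requires focal radiation to have ended at least 2 weeks before first dose. The Synopsis and Protocol Section 3.1.1 carry the same text, so neither copy corrects the other. SAP Section 3.2.1 does not restate the criterion and refers the reader to Protocol Section 3.1.

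Other criteria bear on how 10a should be read:

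- Criterion 12 on surgery: "Patients must have completed any major surgery at least 4 weeks prior to first dose of MIRV".
- Criterion 16 on pregnancy testing: "WCBP must have a negative pregnancy test within the 4 days prior to the first dose of MIRV".
- Exclusion 5d on infection: "Any other concurrent infectious disease requiring IV antibiotics within 2 weeks prior to the first dose of MIRV".
- Criterion 4 defines platinum-sensitive disease as "radiographic progression greater than 6 months from last dose of most recent platinum therapy".

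On adherence, Protocol Section 12.7 says "Each Investigator will be responsible for allowing only those patients who have met protocol eligibility criteria to be enrolled". Both that section and the end of Section 3.1.2 rule out prospective waivers.

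**The concern.** In an inclusion criterion, requiring that something happened *within* a period before first dose means that it must fall inside that period. Criterion 10a therefore puts a ceiling on the time since systemic therapy and no floor under it. A washout rule, which guards against carry-over toxicity and against crediting earlier treatment with a response, needs a floor.

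What is at stake is who is eligible and who is recorded as a deviator. Applied to the letter, a patient with an ample washout fails 10a, while one who stopped treatment days earlier passes. Because waivers are barred, a site cannot obtain a prospective exception to the literal text. SAP Section 5.2.3 states that "A listing of patients with any protocol deviation will be provided for the Safety population", so the direction of 10a affects that listing. It could also reach the Per Protocol population through the open category of other critical or major deviations in SAP Section 4.12.5.

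**Working it through.** The plan gives no figure to reproduce here. The check sets the criteria side by side and adds some day arithmetic.

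**1. How the eligibility list words its time limits**

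| Item | Wording | Effect |
|---|---|---|
| Inclusion 10b, radiation | at least 2 weeks | minimum gap |
| Inclusion 12, surgery | at least 4 weeks | minimum gap |
| Inclusion 16, pregnancy test | within 4 days | must fall inside the window |
| Exclusion 5d, IV antibiotics | within 2 weeks | barred if inside the window |
| Exclusion 8, stroke | within 6 months | barred if inside the window |
| Inclusion 10a, systemic therapy | within 5 half-lives or 4 weeks | read literally, must fall inside the window |

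Minimum gaps are written *at least*, and *within* marks the inside of a window. In an exclusion, *within* bars a recent event. In an inclusion, the same word requires one.

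**2. Size of the literal ceiling**

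- Four weeks = 28 days.
- Five half-lives equal 28 days when the half-life is 28 / 5 = 5.6 days. Below that, the half-life limb is the shorter one and applies.
- The documents give no half-lives for prior drugs. For illustration only, assumed half-lives of 0.5, 1 and 2 days give ceilings of 5 × 0.5 = 2.5, 5 × 1 = 5 and 5 × 2 = 10 days.

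**3. Against criterion 4**

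- Criterion 4 puts progression more than 6 months after the last platinum dose, and the first MIRV dose comes after that progression.
- With the SAP's own month length of 30.4375 days (Section 7.1), 6 × 30.4375 = 182.6 days.
- For a patient whose latest systemic therapy was platinum, the excess over the ceiling is more than 182.6 − 28 = 154.6 days. The gap is more than 182.6 / 28 = 6.5 times the ceiling.
- She cannot satisfy both criteria.

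**4. Who could satisfy the literal text**

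- If 10a covers only the most recent therapy, patients who have just stopped maintenance treatment (9e) or a later non-platinum line (9b) could pass, with no minimum gap.
- If 10a covers every prior systemic therapy, nobody could pass, because 9a and its note require prior platinum in every patient.

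**5. The alternative reading**

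Read as a minimum of 5 half-lives or 4 weeks, whichever is shorter, 10a fits criteria 4, 9, 10b and 12 without conflict.

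**6. Reach into the analysis**

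The Efficacy Evaluable population needs one dose of MIRV and measurable disease at baseline (Protocol Section 10, SAP Section 4.12.3). Compliance with 10a does not enter that definition, so the 28 and 69 evaluable patients, the futility limit of 9 and the rejection rule of more than 26 responders are unchanged.

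**The case against.** The strongest reply is that context already corrects the wording. A ceiling would shut out patients whose last treatment was platinum, in a trial of platinum-sensitive disease, and it would sit beside two minimum gaps. An oncologist would read 10a as no systemic therapy in that period, much as the exclusion criteria use the same phrase. Site practice would then rarely follow the literal text, and no confusion at sites is shown. This stands as a reason to keep the point minor. It does not make the text right: waivers are barred and deviations are judged against what is written.

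A second reply is that the lead-in is not itself at fault. It also governs 10b, which is plainly a minimum, so it can be read as asking only that the listed times be respected. That is fair. The operative defect is in 10a, and changing the lead-in is a matter of clarity.

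A third is that the consequences are thin. SAP Section 5.2.3 promises only a listing, washout is not among the named Per Protocol exclusions, and criteria 5, 11 and 13 (radiographic progression, recovery from toxicity, adequate organ function) limit harm. All of this is correct. Finally, the documents do not record intent, so the case for a minimum rests on inference from the surrounding criteria.

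**Conclusion.** The concern holds, as a minor one. As written, 10a is an upper limit of 28 days or less on the time since systemic therapy. It sets no minimum washout, and none is stated elsewhere. It cannot be met by a patient whose latest systemic therapy was platinum, who exceeds the limit by more than about 154.6 days. That a minimum was meant is inferred from criteria 4, 10b and 12, and the inference is strong.

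The share of patients affected cannot be derived from the documents and is not estimated. There is no effect on alpha, power, the two-stage rule or the primary ORR analysis. The exposure is limited to inconsistent eligibility checks and deviation coding, and to the absence of any stated floor on systemic washout.

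**What to change.** In both the Synopsis and Section 3.1.1, replace *within* in 10a by *completed at least* and leave the rest of the line unchanged, including the sponsor's choice of the shorter of the two intervals. In the criterion 10 lead-in, replace the reference to specified times by *as specified below*, so that it cannot be taken as a ceiling. Classify eligibility deviations against the corrected rule. Even if enrolment is complete, a written clarification would help keep the coding consistent.

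The cost is two lines of text in two places, with no change to design, sample size or analysis.
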